### **b. Sample**

This study examines the socialization experiences of preschool children with LI inclusive classrooms and the entire classroom social network. Thus, we seek to consent all children in each classroom as participants in this study. For children who are not focal children or peers assisting with the intervention, we will seek caregiver consent to observe their children in the classroom and for caregivers to complete a simple questionnaire about their children. We typically are able to actively or passively consent 90% of children in a classroom.

Focal children (n = 30). We describe inclusionary and exclusionary criteria for the 30 focal children with LI. First, we identify all children's positions (n = 495) within the classroom social network using a teacher matrix conducted in fall of the academic year; from this network we calculate a child-level social network index (i.e., individual degree centrality; lower scores are characteristic of social exclusion (Justice, Chen, et al., 2019)). Second, teachers simultaneously complete the Developmental Pragmatic Profile (DPP) (Wiig, Secord, & Semel, 2004) for each child in the classroom. This is a 26-item psychometrically sound checklist assessing children's pragmatic skills (e.g., conversational abilities, giving information), and DPP scores have strong classification accuracy in differentiating children with LI from non-affected classmates (Justice, Ahn, & Logan, 2019). Third, teachers also use a checklist to identify children with LI in each classroom per four criteria: the child (1) is on the caseload of a speech-language pathologist, (2) has no known additional diagnoses causal of LI, such as ASD, (3) primarily communicates in English, and (4) is greater or equal than 42 months of age. Finally, among the children with LI, we select the target child based on the lowest centrality scored weighted by DPP score, so that focal children represent the most socially isolated children with the poorest social-pragmatic communication skills.

### **c. Detailed Study Procedures**

Pilot: Children and teachers participate for a 6 week period, and primary procedures are described here.

Main Study: Children and teachers participate for a 9-month period, and primary procedures are described here.

## **Intervention Implementation**

Pilot: Focal children in the two classrooms participating in the pilot will receive peer-mediated PRT per procedures detailed by Brock et al. (Brock, Dueker, & Barczak, 2018). PRT procedures are facilitated by a classroom facilitator—a classroom teacher or teaching assistant—who will receive ongoing training and support from research staff. Focal children receive peer-mediated pivotal response treatment. With carefully identified classroom peers, facilitators hold four 15-minute training sessions with the peer group, each developing 1 of 4 strategies to use to engage with the target child. The facilitator explicitly identifies the focal child ('buddy') and asks the children to use four strategies to play with the child during center time: a) offer your buddy some play options; b) show and talk about how to play with your buddy; c) compliment your buddy; and d) show your buddy how to take turns. After the trainings are complete, the facilitator provides ongoing support to peers during center time to implement the strategies by regularly encouraging them and supporting them to use the strategies, praising them when they use the strategies well, and reviewing their interactions with the focal child at the end of center time. Facilitators provide this support during center time at least 3 times weekly for the duration of the 6 week pilot.

Main Study: Focal children in OSU-based treatment condition classrooms will receive peer-mediated PRT per procedures detailed by Brock et al (Brock, Dueker, & Barczak, 2018). PRT procedures are facilitated by a classroom facilitator—a classroom teacher or teaching assistant—who will receive ongoing training and support from research staff. Focal children receive peer-mediated pivotal response treatment. With carefully identified classroom peers, facilitators hold four 15-minute training sessions with the peer group, each developing 1 of 4 strategies to use to engage with the target child. The facilitator explicitly identifies the focal child ('buddy') and asks the children to use four strategies to play with the child during center time: a) offer your buddy some play options; b) show and talk about how to play with your buddy; c) compliment your buddy; and d) show your buddy how to take turns. After the trainings are complete, the facilitator provides ongoing support to peers during center time to implement the strategies by regularly encouraging them and supporting them to use the strategies, praising them when they use the strategies well, and reviewing their interactions with the focal child at the end of center time. Facilitators provide this support during center time at least 3 times weekly for a 12-week period.

### **Data collection**

Main Study and Pilot: Classroom social networks will be observed using: (1) researcher observations and (2) location tracking.

Caregivers and teacher surveys and questionnaires will be collected in the following ways 1) recorded on forms that are directly scanned into centralized study databases or 2) via an online TeleForm template accessed through a website link or on a tablet, or 3) via a survey in Qualtrics. All caregiver and teacher-report measures will use web links that automatically feed into a centralized database. Derived scores for specific measures are programmed for automatic computation. We will adhere to the highest standards in data management practices (McCartney, Burchinal, & Bub, 2006) to ensure the integrity of our data, including double-entry for any hand-entered data and regular data audits.

### **d. Measures and Instrumentation**

**Researcher observations.** Researcher observations of peer social interactions are adapted from a validated observation protocol (Schaefer, Light, Fabes, Hanish, & Martin, 2010).

Pilot Study: Using trained, reliable observers blind to study hypotheses and classroom study condition, a ~40-min observation session will be conducted in each classroom once per week during weeks 2-6 of the pilot. The observer will observe the classroom during center time and use the list of peer and focal children to structure four partial interval observation cycles; in each cycle, the observer observes each child for 15 s followed by 15 s recording and then moves to the next child. At the end of one cycle, the observer takes a 5-min break. When observed, each child is recorded for any interaction partners (up to five) based on presence of a verbal or physical exchange or parallel play in the same activity during the 15-s observation. Reliability estimates will be assessed for 10% of cycles via double-coding. Based on researcher

observations, a social network will be created for each classroom per observation window. It will be stored in a symmetric square matrix, where the rows and columns represent the classroom roster and each cell value refers to the frequency at which the pair of children play with each other.

Main Study: Using trained, reliable observers blind to study hypotheses and classroom study condition, a ~40-min observation session will be conducted in each classroom 8-16 times over the academic year. The observer will observe the classroom during center time and use a randomized list of children to structure four partial interval observation cycles; in each cycle, the observer observes each child for 15 s followed by 15 s recording and then moves to the next child. At the end of one cycle, the observer takes a 5-min break. When observed, each child is recorded for any interaction partners (up to five) based on presence of a verbal or physical exchange or parallel play in the same activity during the 15-s observation. Reliability estimates will be assessed for 10% of cycles via double-coding. Based on researcher observations, a social network will be created for each classroom per observation window. It will be stored in a symmetric square matrix, where the rows and columns represent the classroom roster and each cell value refers to the frequency at which the pair of children play with each other.

### **Location tracking.**

Pilot: We augment researcher observations with automated continuous location tracking to capture children's social contact with each other in the classroom. The tracking approach compensates researcher observation by continuously capturing peer social contact across classroom activities and context. For the present purposes, we will use pilot observation to validate the system of indoor location tracking to be used in the main study. For the purposes of the pilot, we will validate a Bluetooth-based identification and proximity detection system only. The Bluetooth tags, also called beacons, will be worn by children and teachers 3 per week during weeks 2-6 of the pilot. The goal is to ensure accuracy and feasibility during the main study.

Main Study: We augment researcher observations with automated continuous location tracking to capture children's social contact with each other in the classroom. The tracking approach compensates researcher observation by continuously capturing peer social contact across classroom activities and context. For the present purposes, we will use a Bluetooth-based identification and proximity detection system for a six-hour period on 8-16 randomly selected observation days throughout the year. A bluetooth beacon and up to two audio recorders will be attached to a vest/pouch that will be worn by children and teachers participating in the study. A set of antennas located in the corners of the classroom will emit radio frequency signals, which will be detected by the tags in each participant vest/pouch. The tags will also communicate with other participants' tags to measure proximity. Based on the patterns of emission and reception of these signals, the bluetooth system identifies and locates each participant in the classroom. The set of location tracks are be analyzed to determine instances and time durations of person-to-person proximity (e.g., child near child, child near teacher). Based on the location information among children, a classroom social network will be created for each observation window.

For the proposed study, researcher observations are executed on days these location recordings occur, so that we can not only triangulate the social network data, but also validate that social networks based on location tracking validly represent authentic forms of peer socialization. Based on each social network generated from either researcher observation or location tracking across the 8-16 timepoints, the social status of each child in the classroom network will be represented by two types of individual centrality indices: degree centrality (i.e., the amount of social interactions directly associated with a child) and eigenvector centrality (i.e., the amount of social interactions directly associated with a child and indirectly associated with the child through their peers, e.g., “friends’ friends”). Classroom network density is also calculated to represent the average interaction intensity in the classroom, with higher values representing a more closely connected classroom network.

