2. To determine the extent to which peer-mediated pivotal response training yields indirect (mediated) effects on the social, behavioral, and linguistic skills of children with LI
3. To determine the extent to which peer-mediated pivotal response training targeting focal children may broadly effect the social network dynamics at the classroom level.

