
we adopt multilevel growth models similar to those described in Aim 1, except with classroom-level social network indices as outcomes and classrooms as the level-2 unit of analysis. With repeated measurements across the school year, the change rates in socialization indices can be estimated for and compared between the intervention period and control period.

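### Aim 3's only named index, whole-classroom density, mixes the focal child's targeted ties with all other ties, so alone it cannot show whether PRT reached the wider network

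*Combined protocol and SAP*

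**What the plan says.** Section II (Background and Rationale), goal 3, sets out to establish how far "peer-mediated pivotal response training targeting focal children may broadly effect the social network dynamics at the classroom level".

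Section III.d (Measures and Instrumentation) builds the researcher-observation network as a symmetric matrix in which "the rows and columns represent the classroom roster and each cell value refers to the frequency at which the pair of children play with each" […]. A second network is built from location tracking. Under Location tracking, the plan defines two individual centrality indices and one classroom index: "Classroom network density is also calculated to represent the average interaction intensity in the classroom". No other classroom-level index is named.

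Section III.g (Data Analysis) handles Aim 3 with growth models like those of Aim 1, "except with classroom-level social network indices as outcomes and classrooms as the level-2 unit of analysis". The contrast is that "the change rates in socialization indices can be estimated for and compared between the intervention period and control period".

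Under Intervention Implementation (main study), the facilitator names one focal child and "asks the children to use four strategies to play with the child during center time". The plan adds: "Facilitators provide this support during center time at least 3 times weekly for a 12-week period". The observation network is recorded in the same setting: "The observer will observe the classroom during center time and use a randomized list of children". Section III.b (Sample) selects the focal child for low centrality, weighted by pragmatic-language score.

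No section computes a network index without the focal child or divides a change in density into focal and non-focal parts.

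**The concern.** Goal 3 sets a narrow target (one child) against a broad effect (the classroom network). Read that way, it asks what happens to ties other than those the intervention acts on. Full-roster density averages both kinds of tie, so one value of the index fits quite different outcomes.

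- A rise may come entirely from the focal child's own row of the matrix, with nothing changed elsewhere.
- A flat result may mean that nothing happened, or that play moved to the focal child and away from other classmates.

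A direct effect on the focal child could then be reported as a broad classroom effect. A loss of contact among the other children, which a school would want to know about, could go unseen in this index.

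**Working it through.** The documents give no power, effect-size or variance figure for density, so there is no figure of theirs to reproduce. The check takes density as the mean cell of the roster matrix.

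**Inputs from the documents**
- One focal child per classroom (III.a).
- Classroom size n. The totals disagree: 900 children / 90 classrooms = 10 (III.a), and 495 / 30 = 16.5 (III.b). Both are used. The figure of 770 children in III.a would give 770/90 = 8.6.

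**Assumed, because the documents do not say**
- r, the strength of a focal tie relative to a non-focal tie at baseline: 0.5, range 0.25 to 1.0.
- g, the proportional rise in focal ties: +100%, range +50% to +200%.
- The number of trained peers: 3, in step 4.

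**1. Share of pairs.** Pairs with the focal child are n−1 out of n(n−1)/2, a share of 2/n.
- n = 10: 2/10 = 20%.
- n = 16.5: 2/16.5 = 12.1%.

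**2. Focal ties rise, other ties unchanged.** The focal share of total tie weight is w = r(2/n) / [r(2/n) + 1 − 2/n], and density rises by w × g. With r = 0.5 and g = 1:
- n = 10: w = 0.100/(0.100 + 0.800) = 0.111, so density rises 11.1%.
- n = 16.5: w = 0.0606/(0.0606 + 0.8788) = 0.0645, so density rises 6.5%.

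Non-focal density changes by 0% in both. The ranges are:

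| Varied | n = 10 | n = 16.5 |
|---|---|---|
| g from +50% to +200%, r = 0.5 | 5.6% to 22.2% | 3.2% to 12.9% |
| r from 0.25 to 1.0, g = +100% | 5.9% to 20.0% | 3.3% to 12.1% |

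**3. Same rise, fully displaced from other pairs.** Full density changes by 0%. Non-focal density changes by −wg/(1−w).
- n = 10: −0.111/0.889 = −12.5%.
- n = 16.5: −0.0645/0.9355 = −6.9%.

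**4. Only three trained peers' ties change.** Take n = 16, so 120 pairs: 15 focal pairs at 0.5 and 105 others at 1. Total weight is 7.5 + 105 = 112.5. Three ties tripling from 0.5 to 1.5 add 3.
- Without displacement: 3/112.5 = +2.7% in full density, 0% in non-focal density.
- With full displacement: 0% in full density, −3/105 = −2.9% in non-focal density.

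**5. Would such a rise reach significance?** As an illustration only, take a simple two-group comparison of 30 against 20 classrooms at two-sided 0.05. A 6.4% rise would be declared significant with probability 0.99, 0.60, 0.20 or 0.11 if the between-classroom coefficient of variation of density were 5%, 10%, 20% or 30%. That coefficient is not given, and the planned analysis is a growth model, so the documents do not settle the question.

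**The case against.** The strongest defence is that Section III.g also describes Aim 3 as testing effects on peer socialization at the classroom level. Full-roster density is a valid total-effect measure for that question. This stands, and it is a reason to keep full density. It does not make density an answer to the broader wording of goal 3.

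Second, the plan already compares centrality trajectories of focal children and classmates under Aim 1, and degree centrality contains the needed information. With S the sum of classmates' degrees and f the focal child's degree, non-focal density equals (S − f)/[(n−1)(n−2)]. Under full displacement, classmates' mean degree would fall. So the data are there, but the plan does not form this combination. Classmates' degree alone is not a clean substitute, because it also counts ties to the focal child: in step 4 without displacement it rises from 217.5/15 = 14.5 to 220.5/15 = 14.7 with no spread.

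Third, location tracking covers six hours and all classroom activities, whereas prompting takes place in center time. This would dilute prompted ties in that network. It bears on size, not on the mixing of ties.

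A reader might also infer stronger claims that the documents do not support:
- That density must rise whenever Aim 1 succeeds. Step 3 shows it can stay flat.
- That Aim 3 merely repeats Aim 1. Between 80% and 88% of pairs do not involve the focal child, so most of the average comes from elsewhere.

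**Conclusion.** The point holds as a matter of interpretation. Full-roster density mixes directly targeted ties with all others, so neither a positive nor a null Aim 3 result can by itself show whether PRT affected the network beyond the focal child. This follows from the plan's own definitions.

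The size is modest and rests on assumptions. A density rise with no spread is about 11% (n = 10) or 6.5% (n = 16.5) if all focal ties start at half strength and double with no displacement. It is about 2.7% if only three ties triple at n = 16. Larger figures need steeper rises in the targeted ties, for which the documents give no basis. It would go too far to say that a positive Aim 3 result would be spurious, or that full density is the wrong outcome.

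**What to change.** In the Aim 3 section of the analysis plan:

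1. Keep full-roster density, labelled as the total classroom effect.
2. Add density among non-focal children, with the focal child's row and column removed. Compute it from the same matrices, for both the observation and the location-tracking networks, in every classroom with a designated focal child, and fit it in the same growth model.
3. State in advance that any conclusion that PRT spread beyond the focal child rests on the non-focal density.
4. Report the focal child's ties separately, split by trained and untrained peers where peers are identified. Removing the whole row also drops ties to untrained classmates, and a rise in those would itself be of interest.

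No new data are needed. The added index uses 12-20% fewer pairs, so it is slightly noisier. Classrooms without a designated focal child do not contribute to it. Sections III.a and III.b name 30 focal children against 90 classrooms, so the plan should say which control classrooms have one. The trained/untrained split may not be available in control classrooms before they start the intervention, since the plan describes no trained peers there.

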## **Focal Child Observations and Assessments**

### **Focal Child observations.**

**Pilot Study:** To ensure we are able to accurately capture this proximal treatment outcome during the main study, we examine focal children’s social interactions with classmates in terms of peer interactions and peer talk. These activities are conducted on the same day as the researcher observations and occur during weekly during weeks 2-5 of the pilot study. For this observation, observers will observe the focal child for 30 minutes during center time and apply a partial interval recording system involving 15 s of observation and 15 s of documentation. Two variables are captured: (1) peer interactions and (2) play interactions. For peer interactions, each interval is coded for whether nonverbal or verbal interaction was directed to or from the focal child. These simply capture the extent to which focal children interact with peers in the classroom. For play interaction, each interval is coded for four possible categories of play: appropriate peer play, appropriate solitary play, inappropriate play, and no play. These observational data are derived to represent the percentage of intervals in which behaviors are coded. Reliability estimates are assessed for 20% of observations via double-coding.

**Main Study:** As a proximal treatment outcome, we examine focal children’s social interactions with classmates in terms of peer interactions and peer talk. These activities are conducted on the same day as the researcher observations and occur 8-16 times annually (three at least 3 during intervention). For peer interactions, we observe the peer interactions of the focal children during observations conducted over the academic year using an established protocol (Brock et al., 2018). These are conducted on the same day as the prior observation (researcher observation), with order randomized. For this observation, observers will observe the focal child for 30 minutes during center time and apply a partial interval recording system involving 15 s of observation and 15 s of documentation. Two variables are captured: (1) peer interactions and (2) play interactions. For peer interactions, each interval is coded for whether nonverbal or verbal interaction was directed to or from the focal child. These simply capture the extent to which focal children interact with peers in the classroom. For play interaction, each interval is coded for four possible categories of play: appropriate peer play, appropriate solitary play, inappropriate play, and no play. These observational data are derived to represent the percentage of intervals in

which behaviors are coded. Reliability estimates are assessed for 20% of observations via double-coding with observers blind to classroom and child condition.

**Peer Talk:** For peer talk, we will record the amount of incoming and outgoing talk focal children experience using a hands-free voice-activated recorder worn by each child in the vest, with audio capture transcending the entire classroom day. Teachers follow a protocol for placing the vest on each child at the start and end of the day. With multiple hours of audio recorded per child, we will process these recordings to capture duration of outgoing/incoming talk with proximate peers using the following process: (i) augment the voice-recorder ability/voice detection/processing algorithms from the Matlab Audio Systems Toolbox to determine if people are speaking, and how long they are speaking; and (ii) use 2D-proximity data from continuous location tracking to parse the audio tracks across time into the cases where there is simultaneous peer proximity and recorded voice (i.e., peer-to-peer talk for some duration of time that we can obtain from stamp data from proximity/audio recording). While our initial plan does not involve transcribing or otherwise capturing the quality of peer talk, we will pursue additional funds to analyze these audio data later.

**Activity: Main Study Only:** The children's and teacher's vest will also house a small accelerometer as a motion sensor. The output of this sensor will be used to detect classroom activities such as running, sitting, and sleeping.

The audio, proximity, and activity data will be processed using machine learning algorithms that will perform speech annotation, speaker diarization and analyzed for word count estimates, automatic transcriptions, sentiment analysis, and classification of the nature of the interactions, including automatic identification of child-directed speech. Some of these programs require pre-trained machine-learning models housed in the OSU-configured cloud-computing provider Amazon Web Services (AWS), i.e., the computations are carried out in AWS servers, while the data remains accessible only to OSU project staff.

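### The peer-talk rule sets no condition on who is speaking, so the facilitator's added coaching speech can inflate peer-talk duration in intervention periods

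*Combined protocol and SAP*

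**What the plan says.** The Peer Talk paragraph under Focal Child observations (III.d, Measures and Instrumentation) gives the target as "duration of outgoing/incoming talk with proximate peers" and sets out a two-step process to reach it. Step (i) applies voice detection "to determine if people are speaking, and how long they are speaking". Step (ii) uses the location data to "parse the audio tracks across time into the cases where there is simultaneous peer proximity and recorded voice". A parenthesis then describes what is kept as talk from peer to peer.

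A later paragraph in the same section says that machine-learning algorithms "will perform speech annotation, speaker diarization and analyzed for word count estimates", and also lists interaction classification and automatic identification of child-directed speech. The Location tracking section has children and teachers wear tags and recorders, and derives child-near-teacher as well as child-near-child proximity.

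Under Intervention Implementation (main study), the facilitator is "a classroom teacher or teaching assistant". After the peer training, "the facilitator provides ongoing support to peers during center time to implement the strategies by regularly encouraging them"; the role also includes praising the peers and "reviewing their interactions with the focal child at the end of center time". This support is given "at least 3 times weekly for a 12-week period".

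Section III.g (Data Analysis) models the duration of peer talk for focal children in Aim 1, with time-specific intervention status as a predictor.

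**The concern.** The target is clear, but the rule for reaching it is broader than the target. Any voice on the recording while a peer is near meets both steps, including an adult's. If adult speech were equally common in all periods, it would add noise and dilute relative differences without favouring either condition. Coaching is different. It is speech that the intervention itself calls for, it takes place among the peers whose proximity opens the counting window, and center time lies within the recorded day.

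The extra counted minutes would then follow the predictor that the Aim 1 model tests. A rise in measured peer talk could not be told apart from the facilitator talking more. Aim 2 would be affected only if peer talk is used as a socialization index. Section III.g takes those indices one at a time without listing them; the Objectives name exposure to peer talk as part of the mechanism.

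**Working it through.** The documents give no figure for peer-talk minutes, facilitator speech or their variability, so there is nothing to reproduce. The check has two parts.

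**1. Does coaching speech meet the stated rule?**

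- Step (i) requires that someone is speaking. Coaching speech meets this.
- Step (ii) requires a peer near the focal child and a recorded voice at the same time. Coaching during shared play, or a review held with the group, can meet this.
- The parenthesis names the result but adds no test of the speaker.
- Diarization, interaction classification, child-directed-speech identification and teacher proximity are all described, but none appears in either step or is tied to peer-talk duration. Nothing says that diarization will label voices as child or adult.

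Followed as written, the rule admits coaching speech.

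**2. How large could the error be?** With no true change in child talk, the relative error in counted minutes on intervention-period recording days is

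error = p × c × (1 − d) / (T + A)

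| Input | Values | Source |
|---|---|---|
| p, share of intervention-period recording days with coaching | 0.6, 1.0 | 3 sessions weekly is in the plan; a 5-day week is assumed (3/5 = 0.6), with recording days selected at random as planned |
| c, captured coaching minutes per coached day | 5, 10, 15 | assumed |
| d, share of coaching that displaces ordinary adult talk | 0, 0.5, 1 | assumed |
| T, child peer-talk minutes per day | 30, 60, 90 | assumed |
| A, ordinary adult minutes counted in every period | 30, 60 | assumed |

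This gives 2 × 3 × 3 × 3 × 2 = 108 combinations.

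- All combinations: 0% to 25%, median 3.2%; 10 exceed 10%, 75 are at or below 5%, and 36 are exactly zero.
- d = 0: 2% to 25% (9 of the 10 above 10% are here).
- d = 0.5: 1% to 12.5%.
- d = 1: 0% throughout.
- Maximum: 1.0 × 15 × 1 / (30 + 30) = 25%.
- Middle case (p = 0.6, c = 10, T = 60, A = 30): 0.6 × 10 / 90 = 6.7% with no displacement; half that, 3.3%, with d = 0.5.

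The error is never negative, and on this grid it is zero only under full displacement. The counts describe the chosen grid; they are not probabilities.

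**The case against.** The strongest reply is that most of the remedy is already in the plan. The audio is to be diarized and interactions classified, and teacher proximity is derived. The parenthesis may also be read as stating what is to be kept, not merely naming it. On that view, one linking sentence and a child/adult label are missing, and the documents do not show that the outcome will be computed without them. Much of this stands: the means exist, and the gap lies in the definition. It does not remove the point, because the only process stated for this outcome has no speaker condition.

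It is also fair that the illustration is weak evidence of importance. Apart from the coaching frequency, its inputs are assumed, most combinations are small, and no documented standard deviation or effect size lets one judge materiality.

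A reader might go further in two ways that the documents do not support:

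- **That adult speech is miscounted only in intervention periods.** The rule admits adult speech in every period and arm, and the facilitator is regular classroom staff. Only the added coaching is specific to intervention periods.
- **That the bias could run in either direction because children may talk less while being coached.** Subtracting up to one minute of child talk per coaching minute would give a net shift of −25% to +25% on the same inputs. Lost child talk, however, is a real change in the outcome. Counted adult speech could partly hide such a fall, but the fall is not measurement error, and that range does not describe this defect.

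**Conclusion.** The point holds as a gap in the outcome definition that should be closed. The stated rule can count the facilitator's added speech as peer talk, and that speech varies with the intervention status tested in Aim 1. The resulting error is upward, or zero if coaching fully replaces ordinary adult talk. Its size cannot be derived from the documents; 0% to 25% with a median of 3.2% is a range over assumed inputs, not an estimate. Confidence is medium, because the planned diarization may in practice be applied to this outcome even though no sentence says so.

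The scope is limited. The observer-coded peer-interaction and appropriate-peer-play outcomes do not use this rule, and Aim 2 is affected only if peer talk serves as a socialization index there.

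**What to change.** Amend step (ii) so that peer-talk duration sums only segments that meet both conditions: the planned diarization, with a child/adult label added, attributes them to the focal child or a proximate peer, and a peer is near at the same time. Apply the same rule in all classrooms and periods, and in Aim 2 if peer talk is used there. The recorders worn by each participant can help attribution.

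Report two sensitivity analyses: the unfiltered duration, and a version that excludes teacher-proximate time. Neither should be primary. The exclusion would also remove genuine peer talk during coached center time, and it may miss coaching by a teaching assistant, who is not stated to wear a tag.

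Check the labels on a small hand-coded sample of study audio from coached and uncoached periods, and report accuracy by period, since labelling error may differ between them. State as a limitation that talk by nearby children not directed to or from the focal child may still be counted.

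The cost is a short change to the definition, an added label, a small coding exercise and extra processing. The main downside is some speaker-labelling error. No new data collection is needed.
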